9.5.2 Safety variables

The assessment of safety will be based mainly on the frequency of adverse events.

Adverse events will be summarized by presenting the number and percentage of patients having any adverse event, having an adverse event in each system organ class and having each

individual adverse event by cohort and overall. Any other information collected (e.g., severity or relationship to fingolimod) will be summarized, as appropriate.

Serious adverse events and adverse events leading to discontinuation of study will be summarized by system organ class and preferred term for each cohort and overall.

Safety Set will be used for the following analyses.

In addition to variables presented in [Section 9.4.1](#), the following secondary variables will be analyzed:

1. Change from Baseline to Months 3, and 12 in CD4+ naïve T cells (CCR7+CD45RA+);
2. Change from Baseline to Months 3, and 12 in CD4+ central memory T cells (CCR7+CD45RA-CD45RO+);
3. Change from Baseline to Months 3, and 12 in CD4+ effector memory T cells (CCR7-CD45RA-CD45RO+);
4. Change from Baseline to Months 3, and 12 in CD4+ Th1 cells (CXCR3+);
5. Change from Baseline to Months 3, and 12 in CD4+ Th2 cells (CCR4+);
6. Change from Baseline to Months 3, and 12 in CD4+ Th17 cells (CCR6+);
7. Change from Baseline to Months 3, and 12 in CD8+ naïve T cells (CCR7+CD45RA+);
8. Change from Baseline to Months 3, and 12 in CD8+ central memory T cells (CCR7+CD45RA-CD45RO+);
9. Change from Baseline to Months 3, and 12 in CD8+ effector memory T cells (CCR7-CD45RA-CD45RO+);
10. Change from Baseline to Months 3, and 12 in naïve B cells (CD19+CD27-);
11. Change from Baseline to Months 3, and 12 in memory B cells (CD19+CD27+);
12. Change from Baseline to Months 3, and 12 in regulatory B cells (CD19+CD24+CD38+);
13. Change from Baseline to Months 3, and 12 in monocytes (CD14+);
14. Change from Baseline to Months 3, and 12 in neutrophils (CD16+);
15. Change from Baseline to Months 3, and 12 in NK cells (CD56+);
16. Change from Baseline to Months 3, 6, and 12 in the anti-JCV antibody index;
17. Change from Baseline to Months 3, 6, and 12 in Hematology measurements;
18. Anti-JCV antibody status (+ or -) at Months 3, 6, and 12.

[figure not shown]
For Variable 18, frequency count and percentage together with the 95% confidence interval for the proportion of JCV antibody positive patients will be presented.

For Variables 1-17, Descriptive statistics (sample size, mean, standard deviation, standard error of mean, minimum, first quartile, median, third quartile, interquartile range, and maximum) will be provided. The 95% confidence interval for the mean will be calculated.

In addition, correlation coefficients between changes in cellular (T, B and monocyte, neutrophil, NK) subsets and efficacy (MRI based variables and PDDS) and safety outcomes (anti-JCV antibody status and index) will be computed. Analyses of safety data will be by cohort based on the Safety Set.

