1.1 Background

Fingolimod is a sphingosine 1-phosphate receptor (S1PR1) modulator approved for relapsing multiple sclerosis (RMS). This mechanism of action has a differential impact on multiple phenotypic subtypes of the immune system. Modulation of S1PRs favors CC-chemokine receptor 7 (CCR7)-mediated retention of naïve T (Tn) cells and central memory T (TCM) cells, including Th17 cells in lymph nodes, thereby reducing the trafficking of potentially autoreactive lymphocytes and preventing their infiltration into the central nervous system (CNS), [Mehling et al 2008, 2010](#). Fingolimod reduces the numbers of CD4+ and CD8+ T cells, the effect being more pronounced for the CD4+ T cell subset, [Song et al 2015](#). In contrast, effector memory T (TEM) cells, which lack CCR7, [Sallusto et al 1999](#) do not regularly circulate through lymph nodes and are largely unaffected by fingolimod, [Mehling et al 2008](#) and [Brinkmann et al 2009](#). The relative sparing of TEM cells, which are important in immune surveillance, together with the preservation of function of sequestered lymphocytes, [Kappos et al 2015](#), [Brinkmann et al 2000, 2001 and 2002](#), suggests that key features of the immune system are maintained during fingolimod therapy. Chronic fingolimod therapy with 0.5mg/day results in lymphocyte counts of approximately 30% of the baseline lymphocyte count, [Chun, J. and Hartung, H 2010](#); [Francis et al 2014](#). However, Absolute Lymphocyte Counts (ALC) during fingolimod therapy is not a marker of immune competence and not related to risk of infections, [Francis et al 2014](#), [Fox et al 2014](#).

In 2015, in the post marketing setting of longer term treated patients, two opportunistic infections Progressive Multifocal Leukoencephalopathy (PML) and Cryptococcal Meningitis manifested at a rare frequency, which led to label changes, [United States package insert \(USPI\)](#). Since these opportunistic infections had not been described until this point, these new findings triggered interest in yet unknown immune system changes in long term continuously treated patients. PML is caused by the John Cunningham virus (JCV) and its development is associated with the presence of anti-JCV antibodies in serum. PML risk can be stratified in seropositive MS patients based on serum anti-JCV antibody levels as measured by the index. The significance of anti-JCV antibody index changes during fingolimod treatment and its relationship to PML risk is unknown.

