3.2 Rationale for study design

The open label, multicenter study used in this study is aligned with the previous Biobank study and its extension (CFTY720DDE01 and CFTY720DDE01E1) performed for the indication of RMS and is in accordance with the health authority guidelines and feedback, including the United States Food and Drug Administration (FDA).

The studies mentioned above evaluated the immune profile of fingolimod treated patients up to 48 months (i.e., Baseline, 1 month, 4 months, 6 months and 48 months). An expected reduction in CD4+ and CD8+ naïve (Tn) and central memory T cells (TCM), as well as CD19+ B cells, persisted up to 48 months. Although CD4+ TEM were spared, a decrease in CD8+ effector memory T cells (TEM) was observed at 48 months. In contrast, CD14+ monocytes and CD56+ NK cells expanded over the course of treatment. These findings have important implications for immune surveillance (i.e., CD8+ TEM reduction) and development of opportunistic infection. While these studies assessed temporal changes in cell subsets during long term

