6.4.9 Biomarkers and Hematology Assessments

Blood samples (approximately 60-80 ml) will be collected as per the Visit schedule outlined in [Table 6-1](#). For each Visit a total of up to 80 ml blood will be drawn (please refer to Laboratory manual) for biomarker and hematology assessments.

Note: In Cohort 1 patients it is critical that the blood sample, must be collected prior to administration of fingolimod, FDO.

A central laboratory will be used for analysis of all specimens collected. A laboratory manual with information on blood sample collection, handling, shipment of samples, processing and reporting of results will be provided.

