2.7 Analysis of the primary objective

2.7.1 Primary endpoint

All analyses will be conducted by cohort for the Safety Set. There are 22 primary endpoints for this study, and Change from Baseline to Month 6 will be calculated as:

Change from baseline to Month 6 = Observed Value at Month 6 (Days 136 to 270) – Baseline Value

1. Change from Baseline to Month 6 in CD4+ naïve T cells (CCR7+CD45RA+)
2. Change from Baseline to Month 6 in CD4+ central memory T cells (CCR7+CD45RACD45RO+)
3. Change from Baseline to Month 6 in CD4+ effector memory T cells (CCR7-CD45RACD45RO+)
4. Change from Baseline to Month 6 in CD4+ Th1 cells (CXCR3+)
5. Change from Baseline to Month 6 in CD4+ Th2 cells (CCR4+)
6. Change from Baseline to Month 6 in CD4+ Th17 cells (CCR6+)
7. Change from Baseline to Month 6 in CD8+ naïve T cells (CCR7+CD45RA+)
8. Change from Baseline to Month 6 in CD8+ central memory T cells (CCR7+CD45RACD45RO+)
9. Change from Baseline to Month 6 in CD8+ effector memory T cells (CCR7-CD45RACD45RO+)
10. Change from Baseline to Month 6 in naïve B Lymphocytes (CD19+CD27-)
11. Change from Baseline to Month 6 in memory B Lymphocytes (CD19+CD27+)
12. Change from Baseline to Month 6 in regulatory B Lymphocytes (CD19+CD24+CD38+)
13. Change from Baseline to Month 6 in monocytes (CD14+)
14. Change from Baseline to Month 6 in neutrophils (CD16+)
15. Change from Baseline to Month 6 in NK cells (CD56+)
16. Change from Baseline to Month 6 in Total CD4+ Absolute Cell Counts
17. Change from Baseline to Month 6 in Total CD4+ Differential Cell Counts
18. Change from Baseline to Month 6 in Total CD8+ Absolute Cell Counts
19. Change from Baseline to Month 6 in Total CD8+ Differential Cell Counts
20. Change from Baseline to Month 6 in Total CD19+ Absolute Cell Counts
21. Change from Baseline to Month 6 in Total CD19+ Differential Cell Counts

Descriptive statistics (sample size, mean, standard deviation, standard error of mean, minimum, first quartile, median, third quartile, interquartile range, and maximum) will be provided. The 95% confidence interval for the mean will be calculated.

Analyses will be performed with respect to the actual value of primary variables by employing an analysis of covariance (ANCOVA) model with gender as a factor and duration of disease at Baseline (either time since first symptom or time since diagnosis) and corresponding baseline as covariates. The unadjusted as well as the adjusted least squares means will be provided together with a p-value.

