5.2.2 Key secondary analysis

The correlation of changes from baseline in cellular (T, B and monocyte, neutrophil, NK) subsets with efficacy (MRI based variables and PDDS) and safety outcomes (anti-JCV antibody status and index) will be estimated within each cohort for each assessment time separately. Analyses involving the MRI based variables or the PDDS will be conducted on the FAS, while analyses of safety outcomes will use the Safety Set.

A Pearson correlation coefficient will be used to estimate the correlation of changes in cellular subsets with changes in T2 lesion volume, changes in PDDS score, and changes in anti-JCV index.

The correlation between changes in cellular subsets and number of new Gd-enhancing T1 lesions will be estimated by a Spearman coefficient.

The relationship between changes in cellular subsets and anti-JCV antibody status (positive or negative) will be assessed using a t-test to compare the mean change in cellular subset across anti-JCV antibody status.

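### In Cohort 1, the efficacy correlations for depleted lymphocyte subsets use raw change in absolute count, which is dominated by the pre-treatment Baseline; a baseline-adjusted coefficient should be reported beside the raw one.

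*Protocol*

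**What the plan says.** - **Planned analysis.** Protocol 9.5.2 calls for "correlation coefficients between changes in cellular (T, B and monocyte, neutrophil, NK) subsets and efficacy (MRI based variables and PDDS"). SAP 5.2.2, headed as the key secondary analysis, gives the methods: "A Pearson correlation coefficient will be used to estimate the correlation of changes in cellular subsets with changes in T2 lesion volume", with Pearson also for PDDS; and "The correlation between changes in cellular subsets and number of new Gd-enhancing T1 lesions will be estimated by a Spearman coefficient". They "will be estimated within each cohort for each assessment time separately". No other stratification or adjustment is named.
- **Definition of change.** It is a simple difference (SAP 2.1.1). For Month 6, SAP 2.7.1 has "Change from baseline to Month 6 = Observed Value at Month 6 (Days 136 to 270") minus the Baseline value. No ratio, logarithm or baseline term enters the correlations.
- **Cohort 1 Baseline.** It is pre-treatment. Protocol 6.4.9: "In Cohort 1 patients it is critical that the blood sample, must be collected prior to administration of fingolimod, FDO".
- **Expected effect.** Protocol 1.1 says chronic therapy "results in lymphocyte counts of approximately 30% of the baseline lymphocyte count". Protocol 3.2, on the earlier studies, reports "An expected reduction in CD4+ and CD8+ naïve (Tn) and central memory T cells (TCM), as well as CD19+ B cells". The same two sections describe effector memory T cells as mostly spared (with a CD8+ fall seen at 48 months) and monocytes and NK cells as rising.
- **Baseline elsewhere.** The primary ANCOVA (Protocol 9.4.1, SAP 2.7.1 and 5.2.1) includes the corresponding baseline as a covariate.

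**The concern.** When a count falls roughly in proportion to its starting level, patients who start high lose more cells even if every patient responds equally. The raw difference then ranks patients mainly by pre-treatment count. Correlating it with PDDS or MRI outcomes mixes two questions: whether the pre-treatment count is related to outcome, and whether the depth of the cellular response is.

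Protocol 3.2 names the missing link between cell changes and clinical efficacy as a limitation of the earlier studies that this one should fill, and Protocol 9.7 allows interim results, including the primary analysis, to be published. Readers may therefore take a Cohort 1 coefficient for naïve T, central memory T or B cells as evidence about drug response when it may reflect only the pre-treatment count. A real link with response could equally appear too weak to notice.

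**Working it through.** **The plan's own figures.** The documents state none for these correlations. The sample-size statement reproduces: a one-sample t-test with n = 200, effect size 0.30 and two-sided alpha 0.05/15 has power 89.6% (stated 89%), and 1.96/√200 = 0.139 (stated 0.14). Neither is affected.

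**Inputs.** From the documents: change = visit value minus Baseline; 30% of Baseline remaining (total lymphocytes); n = 200 per cohort. Assumed, because no SDs or subset-level falls are given: Baseline CV, CV of the on-treatment fraction f, and links of 0.3 with outcome.

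**Step 1: exact case.** If every patient falls to 0.30 of Baseline B, change D = 0.30B - B = -0.70B. Then corr(D, B) = -1, and the correlation of D with any outcome is minus that of B with the outcome.

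**Step 2: general formula.** With k = SD(visit)/SD(Baseline) and ρ = corr(visit, Baseline),

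corr(D, B) = (ρk - 1)/√(1 + k² - 2ρk).

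Equal CVs at both visits and a fall to 30% give k = 0.3:
- ρ = 0: -1/√1.09 = -0.958
- ρ = 0.5: -0.85/√0.79 = -0.956
- ρ = 0.9: -0.73/√0.55 = -0.984

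Over ρ from 0 to 0.9 the range is -0.95 to -0.98, so Baseline explains about 91-97% of the variance of change. At k = 0.5 the range is -0.87 to -0.93.

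**Step 3: varying response.** Simulation with lognormal B, f independent of B, mean f 0.30 and Baseline CV 30-40%:

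| CV of f | corr(D, B) |
|---|---|
| 25-50% | -0.80 to -0.96 |
| 80% | -0.65 to -0.74 |

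Ranks do not remove this. In a companion run with Baseline CV 30%, the Spearman correlation of D with B was -0.95 at a CV of f of 20% and -0.82 at 40%.

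**Step 4: effect on the planned coefficient.** The partial correlation given B is (r_DY - r_DB·r_BY)/√[(1 - r_DB²)(1 - r_BY²)], where Y is the outcome.

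(A) Outcome linked only to Baseline count, r = 0.3. Then r_DY = 0.3 × r_DB, that is 0.3 × (-0.80) = -0.24 to 0.3 × (-0.96) = -0.29. The numerator of the partial coefficient is zero.

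(B) Outcome linked only to log f, r = 0.3. In the companion run at a CV of f of 40%, corr(D, log f) = 0.509 and corr(D, B) = -0.833. So r_DY = 0.3 × 0.509 = 0.15, and the partial r is 0.153/√(1 - 0.833²) = 0.28.

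Simulated results with CV of f 25-50% (2,000 cohorts per setting; approximate):

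| Scenario | n | Raw r: 95% CI excludes 0 | Partial r: 95% CI excludes 0 |
|---|---|---|---|
| A | 200 | 93-99% | 5-6% |
| A | 100 | 68-86% | not tabulated |
| B | 200 | 18-64% | 97-99% |
| B | 100 | 11-37% | 77-84% |

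At n = 200 in B, the raw r averages 0.08-0.16 and the partial r 0.27-0.28. With CV of f at 80% and n = 200, the raw coefficient excludes 0 in about 77-87% of runs in A and 68-78% in B. At n = 50, A gives about 42-54%.

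**Step 5: spared or expanding subsets.** With mean f of 1.0-1.2 and CV of f 30%, corr(D, B) is 0.00 to +0.20. In A the raw r is 0.00-0.06 and excludes 0 in about 6-14% of runs. In B raw and partial coefficients perform alike (96-98%). If instead the two visits simply have equal SDs (k = 1), the formula gives -0.39 at ρ = 0.7 and -0.22 at ρ = 0.9, which is ordinary regression to the mean.

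**The case against.** A reader might infer that every raw change in Cohort 1 is nearly minus the Baseline count. The documents do not support that. The planned correlations also cover monocytes, neutrophils and NK cells. Effector memory T cells are described as mostly spared and monocytes and NK cells as rising; no direction is given for neutrophils. Step 5 shows little or no problem for spared or rising subsets. The 30% figure concerns total lymphocytes under chronic therapy, and no unit is given for the 15 subsets: SAP 2.7.1 separates absolute from differential values only for total CD4+, CD8+ and CD19+. If subsets are reported as percentages, the 70% fall does not carry over. Cohort 2 has no pre-treatment Baseline, so the argument does not extend to it. All of this stands and limits the point.

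A reader might also infer that the raw coefficients would be false. They would not: the SAP sets out to estimate a correlation of changes, and in scenario A that correlation truly differs from zero. Only its reading as depth of response would be wrong, and the documents do not state that reading. No test is specified for these coefficients, SAP 2.7.2 disclaims confirmatory hypotheses, and Table 2-1 lists no efficacy correlation as an objective. This also stands; it makes the matter one of interpretation in a descriptive analysis.

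Finally, the sizes depend on assumptions. No document supports a link of 0.3 between pre-treatment count and outcome, and without one scenario A disappears. MRI is recorded only if available from routine care, so n = 200 is optimistic for the T2 and Gd outcomes. Scenario B does not need the link with pre-treatment count, and the dominance of Baseline in Steps 1 to 3 needs no assumption about outcome.

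**Conclusion.** The point holds for absolute counts of the lymphocyte subsets expected to be depleted in Cohort 1: CD4+ and CD8+ naïve and central memory T cells, and CD19+ B cells. If they fall to about 30% of Baseline, raw change correlates about -0.80 to -0.96 with Baseline under the assumed CVs, and about -0.65 to -0.74 if the on-treatment fraction varies very widely. The planned coefficient is then open to misreading as depth of response, and it can understate a real link with response (0.08-0.16 against 0.27-0.28 in the simulated case). The wider reading, that the whole set of efficacy correlations is invalid, is not supported: spared and expanding subsets are little affected, and percentages may behave differently. The primary ANCOVA already includes Baseline. This is a worthwhile, inexpensive improvement to a secondary descriptive analysis.

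**What to change.** In SAP 5.2.2 and Protocol 9.5.2, report for each subset the partial correlation of cell change with each efficacy outcome given the corresponding Baseline cell value, keeping Pearson or Spearman as already assigned. Show it beside the raw coefficient, and base any Cohort 1 statement linking cellular response to efficacy on the partial one. State for each subset whether the values are absolute counts or percentages.

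One rule can serve all subsets, since adjustment loses essentially no power where a subset is spared or rises. A log ratio is a possible supplement but not a substitute: with equal log-SDs at both visits and ρ of 0.3 to 0.9, it still correlates -0.59 to -0.22 with log Baseline.

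The cost is SAP and protocol wording, a PARTIAL statement in SAS PROC CORR and one extra column of coefficients. Baseline values are already collected.

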9.5.3 Biomarkers

See Sections [9.4.1](#), [9.5.1](#) and [9.5.2](#)

9.7 Interim analyses

As previously mentioned, two interim analyses of data will be performed prior to the final analysis at Month 12.

1. The first interim analysis is an early assessment to evaluate safety of Cohort 2 patients. This will be conducted when 50% of patients in Cohort 2 have completed the Month 6 follow up. For this analysis, primary variables, demographics, baseline characteristics, adverse events, and serious adverse events will be summarized.
2. The second interim analysis is the primary analysis for this study. This analysis will be conducted when all patients in Cohorts 1 and 2 complete Month 6 (primary time point of interest) of study. All data collected on patients from both Cohorts 1 and 2 will be included in this analysis. These data will be analyzed as mentioned in Sections [9.4](#), [9.5](#), and [9.6](#).

This is an open-label, single arm study, and has no active control. The first interim analysis is a summarization of data from Cohort 2 only and no confirmatory hypothesis will be tested. Thus, the multiplicity adjustment of the level of significance for the primary analysis due to the first interim analysis is not relevant in this study. Results obtained from these interim analyses may be reported and published externally for communication to health care professions, as appropriate.

9.8 Sample size calculation

Cohort 1: A sample size of 200 patients will be able to detect an effect size of 0.30 with 89% power after adjusting for multiplicity of testing changes in 15 primary variables, at an overall significance level of 0.05.

In addition, for both cohorts the primary interest is to estimate mean change from Baseline at various time points (Months 3, 6, and 12) of the primary and secondary variables. A sample

size of 200 patients in each cohort will provide us the precision of estimates within 0.14 of the corresponding standard deviation of the variables of interest.

10 Ethical considerations

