3.6 Risks and benefits

The study involves a FDA approved dose (0.5mg/day) and indication (RMS) of fingolimod. Therefore the study population will be examined within a known benefit/risk profile of fingolimod. Any procedural risks will be minimized using compliance with the eligibility criteria as well as optimal study procedures.

Patients will receive the benefit of being systematically monitored over a 12 Month period at regular follow-ups for immune phenotype profiling, which would not have taken place during normal routine follow up Visits.

4 Population

The study population will consist of male and female patients (≥ 18 years of age) with a diagnosis of MS. In the first cohort approximately 200 patients with RMS, who are newly prescribed commercially available fingolimod 0.5mg/day will participate in the study. In the second cohort approximately 200 RMS patients who have been on commercially available fingolimod 0.5mg/day continuously for at least ≥ 2 years will participate in the study.

The goal is to include 400 patients (Cohort 1, n=200 and Cohort 2 n=200) from up to 125 centers in the United States. Since a 25% screen failure rate is expected, approximately 533 patients will be screened.

Patients who discontinue after they have been enrolled will not be replaced.

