6.4.7 Magnetic Resonance Imaging Review

Magnetic Resonance Imaging data, if available from standard of routine care will be reviewed and standard MRI measures as outlined below will be recorded in the eCRF at the Visits as outlined in [Table 6-1](#).

- Change from Baseline in T2 lesion burden
- New Gadolinium (Gd)-enhancing T1 lesion count;

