9.5 Analysis of secondary variables

Secondary variables consist of both efficacy and safety variables.

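### The 89% power and 0.14 SD precision hold for 200 evaluable patients, but 200 is the number enrolled per cohort, and the precision sentence also takes in MRI measures that depend on routine scans

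*Protocol*

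**What the plan says.** Protocol 9.8 makes two statements, both repeated in the protocol summary and in SAP section 3.

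- **Power, Cohort 1.** "A sample size of 200 patients will be able to detect an effect size of 0.30 with 89% power after adjusting for multiplicity", the adjustment being for "testing changes in 15 primary variables, at an overall significance level of 0.05". Protocol 9.4.1 defines those 15 variables as blood-cell changes from Baseline to Month 6.
- **Precision, both cohorts.** The stated aim is to "estimate mean change from Baseline at various time points (Months 3, 6, and 12) of the primary and secondary variables", and the section says that a sample "size of 200 patients in each cohort will provide us the precision of estimates within 0.14 of the corresponding standard deviation".

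Other sections determine how many patients will contribute a value:

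- Protocol section 4 sets enrolment at 200 per cohort, 400 in all. It allows for a 25% screen failure rate by screening about 533, and then states: "Patients who discontinue after they have been enrolled will not be replaced".
- Protocol 9.4.3 and SAP 2.7.3 and 2.8.3 rule out imputation of missing efficacy and safety values.
- Protocol 9.5 says: "Secondary variables consist of both efficacy and safety variables". Protocol 9.5.1 lists T2 lesion burden and new Gd-enhancing T1 lesion count among the efficacy variables.
- On those two measures Protocol 6.4.7 says: "Magnetic Resonance Imaging data, if available from standard of routine care will be reviewed". The assessment schedule (Table 6-1) carries the same condition.

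Neither document gives an expected rate of dropout, missed samples or MRI availability.

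**The concern.** The number in the sample size section is the number enrolled, while power and confidence interval width depend on the number with both a baseline and a follow-up value. The plan itself foresees loss between the two: it has a discontinuation visit, a loss-to-follow-up rule and disposition tables. The Safety Set, on which the primary analysis runs, requires only one dose during the study, so its size is not the number with a Month 6 value.

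The precision statement matters because Protocol 9.8 calls estimation the primary interest in both cohorts, and Protocol 3.5 and 9.7 foresee publication. A reader would take 0.14 SD as the planned precision at Months 3, 6 and 12 for every primary and secondary variable, MRI measures included. No scan is required by the protocol, so nothing in the design secures that for MRI.

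**Working it through.** **Inputs**

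- n = 200, standardised effect d = 0.30, overall alpha 0.05, 15 variables (Protocol 9.8).
- Two-sided tests (SAP 2.1).
- Not stated in the documents, so assumed: a one-sample t-test on the change, and Bonferroni adjustment, alpha = 0.05/15 = 0.00333.

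**Formulas**

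- Power = P(|T| > t(1 − alpha/2, n − 1)), where T is noncentral t with n − 1 df and noncentrality d·√n.
- 95% CI half-width in SD units = t(0.975, n − 1)/√n.

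**Step 1: the plan's own figures at n = 200**

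- Noncentrality 0.30 × √200 = 4.243; critical value 2.971; power 89.6%. Šidák adjustment gives 89.8%, alpha rounded to 0.003 gives 89.0%, and the normal approximation gives 90.4%. No adjustment (98.8%) and one-sided Bonferroni (93.2%) do not fit.
- Half-width 1.972/√200 = 0.139 SD.

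Both stated figures reproduce, with all 200 counted as evaluable.

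**Step 2: what the existing inflation covers**

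400/(1 − 0.25) = 533. This covers loss before enrolment only, and leaves 200 enrolled per cohort.

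**Step 3: how much slack there is**

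- Power: n = 197 gives 89.1% and n = 196 gives 88.8%, so the t-test figure falls below 89% once more than 3 of 200 patients lack a value. By the normal approximation the threshold is n = 193.
- Half-width: n = 186 gives 0.1447 and n = 185 gives 0.1451, so 0.14 survives rounding up to 14 of 200 lost (7%).

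**Step 4: figures under assumed loss**

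| Assumed loss | n | Power (0.05/15) | Half-width (SD) |
|---|---|---|---|
| 0% | 200 | 89.6% | 0.139 |
| 5% | 190 | 87.5% | 0.143 |
| 10% | 180 | 85.1% | 0.147 |
| 15% | 170 | 82.3% | 0.151 |
| 20% | 160 | 79.1% | 0.156 |

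**Step 5: MRI, precision statement only, under assumed availability**

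| Assumed availability | n | Half-width (SD) |
|---|---|---|
| 75% | 150 | 0.161 |
| 50% | 100 | 0.198 |
| 25% | 50 | 0.284 |

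Change in T2 lesion burden needs a baseline and a follow-up scan, so its usable n can be lower than availability at a single visit.

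**The case against.** **There is no arithmetic error.** This stands. The sentences say what a sample of 200 provides, and the numbers are right for 200 evaluable patients. A reader might infer that the figures were miscalculated; they were not. What is missing is the condition they rest on.

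**The shortfall is not demonstrated.** A reader might infer that the design fails to deliver its figures. The documents give no loss rate, so that cannot be shown. At an assumed 10% loss the change is modest. The exact threshold of 197 also depends on a test and an adjustment method that Protocol 9.8 does not name.

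**Missing values may be fewer than dropouts.** This stands in part. Protocol section 6 schedules a discontinuation visit with blood sampling and says missed visits should not lead to automatic discontinuation. SAP 2.7.1 accepts Month 6 values from Day 136 to Day 270. But SAP 2.1.1 assigns samples from Days 2 to 135 to Month 3, so a patient who leaves before Day 136 still yields no Month 6 value.

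**The adjusted power may not describe the planned tests.** SAP 2.7.2 says multiplicity adjustment is not relevant, and SAP 2.1 sets tests at two-sided 0.05. At that level the power for d = 0.30 is 98.8% at n = 200, 96.5% at n = 160 and 90.3% at n = 120. So it does not follow that the power of the tests as the SAP would run them is below 89%. The point here concerns the stated figure, which is explicitly adjusted for 15 variables. The conflict between the two SAP sections is a separate matter.

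**MRI may lie outside the precision sentence.** This is arguable. The sentence speaks of mean change at Months 3, 6 and 12, which matches the blood-variable list in Protocol 9.5.2. Protocol 9.5.1 attaches no months to the MRI measures, a new-lesion count is not a change from baseline, and Table 2-1 lists no MRI endpoint. But Protocol 9.5 counts efficacy variables as secondary, and the precision sentence covers secondary variables without exception. The wording should settle this.

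**Achieved n and confidence intervals will be reported.** True, and most analyses are descriptive. That limits the consequence, but does not make the planning statement accurate.

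**Conclusion.** The point holds in a limited form. The 89% power (Cohort 1, Month 6, alpha 0.05/15) and the 0.14 SD precision are correct for 200 evaluable patients, but are presented as what 200 enrolled patients provide, with no replacement, no imputation and no allowance for loss after enrolment. They hold only if almost no one is lost.

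Across an assumed 10% to 20% loss, power is 85% to 79% and the half-width 0.147 to 0.156 SD. These rates are illustrations. The power values also assume a t-test with Bonferroni adjustment, which the documents do not name.

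The precision sentence as worded is not supported for MRI measures. A reader might carry this over to the power statement, but none of the 15 primary variables is an MRI measure, so MRI availability leaves the 89% untouched.

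**What to change.** In the protocol summary, Protocol 9.8 and SAP section 3:

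1. Label both figures as applying to 200 evaluable patients per cohort.
2. State an expected loss by Month 6, and by Month 12 for precision, with the figures at the resulting n. For illustration: n = 180 gives 85% and 0.147 SD; n = 160 gives 79% and 0.156 SD.
3. Limit the 0.14 SD sentence to the blood-based variables, and add that precision for the MRI measures depends on the number of patients with usable scans.

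No extra patients, visits or procedures are needed. The only cost is that the stated figures become slightly less favourable. If the sponsor would rather keep 200 evaluable per cohort, enrolment would have to be 200/(1 − loss): 223 at 10% or 250 at 20%. Given the descriptive aim, restating the figures is enough.
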